Typically, this is a trivial requirement, as CT scans are used ubiquitously to definitively diagnose EDH and SDH, readily and reliably triaging patients to surgical versus medical management. With 97% sensitivity, 98% specificity, 97% positive predicative value, 95% negative predictive value, and 96% accuracy in diagnosing intracranial hematomas, CT scanning is exquisitely effective at identifying or ruling out acute extra-axial, intracranial bleeds in patients who sustain head trauma, making it a gold standard in acutely assessing TBI (2). As a result, head CT has become commonplace, if not universal in assessing head trauma in industrialized countries, where virtually every hospital has one, if not a dozen scanners. In less than 10 minutes, a CT scan can noninvasively prove or reject acute intracranial bleeding. They provide immediate insight into 1.) Whether there is in fact an intracranial bleed; 2.) In the case of a bleed, where below the cranium it has occurred and 3.) When done serially, gauge evolution, resolution, or stability of a bleed. This is invaluable information that directly impacts survival, as failure to perform a craniotomy in a patient with a rapidly expanding intracranial hematoma can swiftly lead to irreversible brain damage or even death. Moreover, performing such a surgery in the wrong location or in a patient who does not have a bleed amenable to surgical intervention can contribute extensive morbidity, exacerbating a patient's already tenuous mortality.

Infrascanner Study PI: [name]

In less developed countries, CT scanners are often difficult to obtain in a timely manner. When they are present, they are extremely meager in number, peppered across treacherous geography, with scant transportation and emergency infrastructure. Even when accessible, they are frequently decommissioned due to a broken part, and are extremely cost prohibitive, with a single scan often costing the equivalent to multiple months' income for the populations who need them most. As a consequence, in the settings where TBI pervades and brain imaging is most critical to survival, obtainment of such imaging is often unachievable.

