A few years ago, the InfraScanner 2000TMwas introduced, prompting our group to validate it in a consecutive series of 500 head injury patients who obtained a head CT scan at Duke University Hospital (DUH). For all patients with CT-proven bleeds (n=104), irrespective of size, initial NIRD scans localized the bleed to the appropriate quadrant with a sensitivity of 86% and specificity of 96% compared to CT scan. For extra-axial bleeds >3.5ml, sensitivity and specificity were 94% and 96%, respectively. For longitudinal serial rescans with the NIRD, sensitivity was 89% (<4 days from injury: sensitivity=99%) and specificity was 96%. For all patients who required craniectomy or craniotomy, the device demonstrated 100% sensitivity.

Infrascanner Study PI: [name]

With these results, the Duke Global Neurosurgery and Neurology (DGNN) proposes to initiate a trial to replicate our DUH findings at MRRH: using the Infrascanner 2000TM in the background of the current standard of care to quantify the accuracy of the device – the positive and negative predictive values – in diagnosing SDH/EDH relative to CT in the Ugandan setting.

We hope that, with positive results, this work can lay the foundation for a subsequent trial using the device to diagnose intracranial bleeds when CT scans cannot be accessed in a timely manner. Such a result could ostensibly improve neurocritical and neurosurgical care in Uganda when obtainment of a CT scan is not feasible in a rapidly deteriorating patient.

As the sensitivity and specificity in detecting traumatic intracranial hematomas approaches that of CT scanning, the prospect of using the InfraScanner 2000TM as a stand-alone diagnostic device for intracranial hematomas in low-resource settings that lack CT scans is highly intriguing. In geographical locations where TBI burden is highest and need for emergency craniotomies is most pressing, the inability to obtain CT scans precludes hundreds to thousands of life-saving surgeries everyday. The use of a handheld device that can be used repeatedly to reliably diagnose and track intracranial bleeding at no cost to a patient could revolutionize the prognosis of TBI for the majority of the 10 million people it affects annually.

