This project intends to show that the InfraScanner 2000TM is capable of detecting and ruling out intracranial hematomas in TBI patients at MRRH at rates similar to CT scan (i.e. replicate the results we have demonstrated at DUH in the Ugandan patient population). This work will hopefully justify initiation of a future trial using the InfraScanner 2000TM as a definitive diagnostic tool in determining surgical versus medical management in CT-barren settings, such as Uganda where our group, DGNN has been building neurosurgical and neurological care capacity over the past decade.

Aim 1: Determine whether the InfraScanner 2000[™] detects epidural and/or subdural hematomas with adequate precision relative to CT scans to be used as a diagnostic tool for epidural and/or subdural hematomas.

Aim 2: Use these findings to inform the feasibility of conducting a future trial in which the InfraScanner 2000TM is used as a stand-alone diagnostic tool for intracranial hematomas, and therein, to determine candidacy for decompressive craniotomies in patients who suffer TBIs in places where CT scans are not available.

4. Background and Significance: Traumatic brain injury (TBI) is a steadily growing global pandemic responsible for immense mortality and morbidity, particularly in low- and middle-income countries (LMICs). The World Health Organization (WHO) estimates that more than 10 million people sustain TBI resulting in death or significant irreversible deficits annually, the majority occurring in resource scarce settings. Most recent approximations suggest that Sub-Saharan Africa (SSA) bears the highest incidence of road traffic injury (RTI)-associated TBI in the world. At a frequency of 170 per 100,000 people, TBI in SSA occurs at a rate 1.5

Infrascanner Study PI: [name]

times that of the global average (1). A great preponderance of these injuries is comprised by intracranial hematomas; injuries that would often stand to benefit from surgical intervention. However, the virtual nonexistence of CT scanners in the majority of settings where these injuries occur, preclude countless patients from receiving life-saving surgery.

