With a median age of 15.7 years, Uganda is second only to Niger in youth of its population. Currently, 69% of the Ugandan population is under the age of 25, and an estimated 80% of all Ugandans between 20 and 30 years earn a living by taxiing passengers. Granted the already globally unprecedented motorbike usage, the cultural ambivalence toward helmets, haphazard law enforcement, and still increasing motorbike density, the already appalling incidence of TBI is inevitably going to upsurge in coming years.

In Uganda, there are currently 33 ICU beds, 6 government neurosurgeons, and 1 formally trained neurologist to serve, not accounting for the significant international referrals received from neighboring countries, the entire population of 41 million people (18, 19). Despite the profound dearth of care and exceptionally high mortality, Africans pay significantly more out of pocket for medical care than the world (83% versus 26%), which in the case of current TBI care, often leads to incurrence of significant familial hardship for improbable survival (14). This constellation of unmatched mortality, resource famine, and debt incurrence fashion SSA, and MRRH in particular, the ideal setting to pilot a minimal-resource, guideline-driven ICU system. The InfraScanner 2000TM can potentially serve as the centerpiece of such a system providing near-zero-cost, immediately-available, sequential intracranial imaging to help make urgent surgical and medical decisions that can save an untold number of lives that are currently being forfeited due to lack of imaging.

To work toward this, this study proposes to validate the high sensitivity, specificity, accuracy, and precision of the InfraScanner 2000TM in detecting traumatic intracranial bleeds we have previously demonstrated at DUH in patients presenting to MRRH. If able to detect intracranial hematomas with efficacy similar to CT in the Ugandan patient population, this data can be used to formulate a future trial using the device as a diagnostic tool to inform medicosurgical management for patients in which obtainment of CT scans is not feasible.

Infrascanner Study PI: [name]

5. Design, Procedures and methods:

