- **13. Costs to the Subject:** No additional costs to the patient will be incurred as a result of this add-on research protocol. The participant will receive UGX 15000 as stipend for participating in the study.
- **14. Statistical Considerations:** Objectives: The primary objective of this study is to estimate the test characteristics (sensitivity, specificity, and the false positive and false negative rates) of the portable NIR-based device (InfraScanner 2000TM) in the identification of any size hematoma among patients hospitalized at MRRH who have sustained or who are suspected to have sustained head trauma. For those who go on to obtain CT scans, the results of the CT scan(s) will serve as the gold standard. The sensitivity, specificity, and the false positive and false negative rates will be estimated at the patient level and at the scan level. Approximately 10% of patients are anticipated to have more than one CT scan.

A secondary objective is to estimate the test characteristics of the InfraScanner 2000TM in identification of hematomas within its detection limits (volume >3.5 mL and depth <2.5 cm) compared to CT scan results as the gold standard.

Exploratory objectives include:

- 1. Examining the impact of factors such as hematoma type, location, and patient age on test characteristics of the InfraScanner 2000TM
- 2. Determining the minimum resolution detectable by the InfraScanner 2000TM
- 3. Analyzing the effects of extracranial hematomas, lacerations, and swelling on the performance characteristics of the device
- 4. Estimating Receiver Operating Characteristic (ROC) curves with patient and scan as the units of analysis (20).

Study Design:

a) Eligibility: All patiets with suspected TBI and meet the WHO and Brain Injury (BI) trust criteria for CT scaning

Inclusion criteria

Patients with suspected TBI above 12 years with suspected TBI and meet the BI criteria for CT scan

Patients that present with CT that was taken within 30 minutes

Patients with TBI that occurred more than 48 hours

Patietns with suspected TBI who present to Mayanja Memorial Hospital for CT scan but managed at Mbarara Regional Referral Hospital

Patients who do not present with CT scan images and cannot afford to pay for a CT Scan, will be included in the study and the study team will pay for their scans.

Exclusion Criteria

Infrascanner Study PI: [name]

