Patients who present died Patients with images other than Mayanja Memorial Hospital and Mbarara Regional Referral Hospital

b) Standard of comparison:

All patients entered into the trial will undergo at least one cranial scanning using the InfraScanner 2000TM at the time of presentation. For patients who go on to get a CT scan, they will be scanned using the InfraScanner 2000TM within 30 minutes of each subsequent CT. Patients and care providers will be blinded to the results of InfraScanner 2000TM. The standard for comparison will be determined as follows. A CT result that is positive for hematoma will be considered a true positive and a CT result that is negative for hematoma will be considered a true negative. For patients who never go on to obtain a CT scan, their InfraScanner 2000TM results will be analyzed in the context of clinical data.

Definitions of Sensitivity, Specificity, False Positive, False Negative: Let A^+ denote the event that the test is positive for hematoma and B^+ denote the event that a hematoma is present. Sensitivity, $P(A^+/B^+)$, will be defined for each patient (scan) as the probability that a true hematoma as determined by CT scan will be detected (21). Similarly, let A^- denote the event that the test is negative for hematoma and B^- denote the event that a hematoma is not present. Specificity, $P(A^-/B^-)$, will be defined as the probability of being negative for hematoma on the InfraScanner 2000TM scan within 30 minutes of CT given the patient has no hematoma present.

The false positive rate will be defined as $P_{F^+} = P(B^-/A^+) = P(A^+/B^-)[1-P(B^+)]/P(A^+)$. Similarly, the false negative rate will be defined as $P_{F^-} = P(B^+/A^-) = [1-P(A^+/B^+)]P(B^+)/[1-P(A^+)]$. Estimates for the false positive and false negative rates will be provided for a range of values for the prevalence of hematomas.

c) Sample Size

Computation of the required number of patients is based on estimating the sensitivity of each method to within at most \pm 0.10 with 90% confidence. The 90% confidence interval for the sensitivity is given by $P_{Sens} \pm$ 1.645*SE(P_{Sens}) where SE(P_{Sens})= [(P_{Sens})(1- P_{Sens})/N; N denotes the number of true positives.

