16. Privacy, Data Storage, and Confidentiality: Participants will be given as research numbers. Data will be stored on secured Qualtrics database and de-identified CT scans stored in a secure box folder. For analysis, data will be fully de-identified. Research materials will be stored in a locked cabinet in the Neurosurgery office in the Department of Neurosurgery and in digital form on the DHTS-maintained server.

17. Limitation of study

The study does not take into account those with brain swelling and contusions which may affect the outcome.

18. Data Sharing Plan

[figure not shown]
Data from this study will be shared equally by the principal investigators. We plan to publish to papers from this work. For the first paper first author will be a local investigator and will also be the corresponding author (Either [name] or [name]). The author will be an international Investigator ([name] or [name]), the same order will be followed for the last authors. The order will change for the second paper.

Infrascanner Study
PI: [name]

Image A (20)

Image B (20)

[figure not shown]

Head location of Infrascanner measurements

[figure not shown]
Frontal Left/Right forehead, above the frontal sinus

Temporal In the Left/Right temporal fossa

Parietal Above the Left/Right ear, midway between the ear and the midline of the skull Occipital Behind the Left/Right ear, midway between the ear and the occipital protuberance

Target Tissue
Simulated photon diffusion path through target tissue from source to detector.

Absorption of light by oxygenated and deoxygenated hemoglobin

References

- 3. Robertson CSGSPCB. Use of Near-Infrared Spectroscopy to Identify Traumatic Intracranial Hematomas. Journal of biomedical optics. 1997;2:33-41.

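### With CT as the reference standard, the study can estimate the device's agreement with CT but cannot show that its accuracy is similar to CT's

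*Combined protocol and SAP*

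**What the plan says.** Section 3 (Purpose of the Study) states the intended demonstration: detection and exclusion of hematomas "at rates similar to CT scan (i.e. replicate the results we have demonstrated at DUH in the Ugandan patient population". The last paragraph of Section 4 repeats it as the condition for basing a later trial of the device as a diagnostic tool on these results: "If able to detect intracranial hematomas with efficacy similar to CT in the Ugandan patient population".

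Section 14 (Statistical Considerations) is more modest. The primary objective is to estimate test characteristics for hematoma of any size, and where CT is obtained, "the results of the CT scan(s) will serve as the gold standard". Section 14 b) makes this a rule: "A CT result that is positive for hematoma will be considered a true positive", with the mirror-image rule for negatives. Section 14 c) sizes the study for precision only. No hypothesis test, similarity margin or minimum performance is given.

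The comparison figures are in Section 3. For CT: "With 97% sensitivity, 98% specificity, 97% positive predicative value, 95% negative predictive value, and 96% accuracy in diagnosing intracranial hematomas". For the device at DUH, over all CT-proven bleeds: "initial NIRD scans localized the bleed to the appropriate quadrant with a sensitivity of 86% and specificity of 96% compared to CT scan". The DUH figures above 3.5 mL, limited to extra-axial bleeds, were 94% for sensitivity and 96% for specificity.

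**The concern.** A claim that two tests perform similarly needs the error rates of both, measured against something outside them, and a statement of how close is close enough. Here one of the two tests is itself the truth. Any disagreement is charged to the device, and CT's own errors cannot appear.

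The parenthesis in the Section 3 sentence then offers replication of DUH as the meaning of similarity. The DUH any-size sensitivity was 86%, so a result near that value could be reported as similar to CT although the data give no basis for the word. What is at stake is the reading of the results. The protocol hopes the work will support a later trial in which the device, without CT, helps decide between surgical and medical management.

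**Working it through.** **1. The plan's own figures (Section 14 c).** Half-width = 1.645 × √(p(1−p)/N), at the worst case p = 0.5.
- N = 68: 1.645 × √(0.25/68) = 0.0997. The plan gives 0.099.
- N = 272: 1.645 × √(0.25/272) = 0.0499. The plan gives 0.05.
- 68/0.20 = 340 with CT; 340/0.50 = 680; 680/0.95 = 716. The plan gives 720.

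The sample size reproduces, apart from rounding, as a precision calculation.

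**2. What the reference rule allows.** Write B+ for hematoma present. Section 14 b) sets B+ equal to CT positive and B− equal to CT negative. Then P(CT+ | B+) = 1 and P(CT− | B−) = 1 whatever the data show. The device's sensitivity is the share of CT-positives that it flags, and its specificity is the share of CT-negatives that it clears. Both measure agreement with CT. Neither can be set against a CT error rate, because the study produces none. This step needs no numbers.

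**3. Replicating DUH for the primary target.** Inputs: sensitivity 0.86 (Section 3) and 68 positives (Section 14 c).
- 1.645 × √(0.86 × 0.14/68) = 0.069, so the 90% interval is 0.791 to 0.929.
- Clopper-Pearson 90% intervals: 0.763 to 0.918 for 58/68, and 0.780 to 0.929 for 59/68.
- Expected misses: 0.14 × 68 = 9.5, so about 9 or 10 CT-proven hematomas.

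The upper limit 0.929 lies 4.1 points below the 97% quoted for CT.

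**4. How far that exclusion reaches.**
- Sensitivity 94% above 3.5 mL. The subgroup size is not given, so it is assumed. The 90% Wald intervals are 0.893 to 0.987 (n = 68), 0.885 to 0.995 (n = 50), and 0.873 to 1 (n = 34, capped at 1). All contain 0.97.
- Specificity 96%, n = 272. The 90% Wald interval is 0.9405 to 0.9795, just below CT's quoted 98%. The 95% Wald interval is 0.937 to 0.983 and contains it.

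**5. DUH's own uncertainty.** With 104 CT-proven bleeds, 0.86 ± 1.645 × √(0.86 × 0.14/104) gives 0.804 to 0.916.

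**The case against.** The strongest reply is that the operative parts of the protocol are sound. The opening purpose is to determine sensitivity, specificity and predictive values. Aim 1 is framed relative to CT, the primary objective is estimation, and no similarity test is planned. On that view the parenthesis simply defines similarity as reproducing DUH's agreement with CT, and the sentence is only a poor label. Much of this stands: neither the design nor the sample size is at fault, and the language about a future trial is hopeful rather than a binding decision rule. It does not rescue the wording. Sections 3 and 4 still state an intended conclusion that Section 14 cannot deliver.

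A reader might go further and infer that replicating DUH would disprove similarity to CT, because the interval excludes 97%. The documents do not support that:
- By its title, the source cited for CT's 97% (reference 2) is "Computed Tomographic Evaluation of Traumatic Epidural and Subdural Haematoma with Post Operative Correlation". CT was apparently judged against operative findings there, whereas the device figures are judged against CT. The two are not on one scale.
- Only the any-size sensitivity clearly excludes the CT figure. The result above 3.5 mL does not, at any subgroup size assumed.
- The 86% is quadrant localisation among all CT-proven bleeds. This study defines sensitivity as detection per patient or scan, and its 68 positives are subdural or epidural hematomas.
- The 11-point gap between 86% and 97% should not be set against the planned ±0.10. That is a worst-case half-width at p = 0.5, not a similarity margin; at 86% the half-width is 0.069.

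The reverse inference fails too. An interval that contains 97% does not show similarity when no margin has been set.

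**Conclusion.** The concern holds as a mismatch between the stated conclusion and what the analysis can show. With CT as the truth by rule, the study can estimate agreement with CT. It cannot show accuracy similar to CT's, and this follows from Section 14 b) without any calculation.

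The arithmetic is supporting evidence only. For the any-size primary target, full replication of DUH means a 90% interval of 0.79 to 0.93 and about 9 or 10 misses among 68 positives, so treating replication as similarity to CT is doubtful on the protocol's own figures. That rests on two assumptions: that the DUH 86% carries over to patient-level detection, and that 68 positives are obtained. CT's 97% serves as an illustrative benchmark and no more. The estimation objective and the sample size need no change.

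**What to change.** In Sections 3 and 4, replace the wording on similarity to CT with: *to estimate sensitivity and specificity with CT as the reference standard, with 90% confidence intervals*. Add one sentence stating that no claim of similarity or equivalence to CT will be made.

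Present the DUH values descriptively beside the new estimates, with DUH's own intervals (for the any-size sensitivity, 0.80 to 0.92 at 90%). Match the definitions, or state where they differ:
- quadrant localisation against patient- or scan-level detection;
- extra-axial bleeds above 3.5 mL at DUH against the secondary objective's limits of volume above 3.5 mL and depth below 2.5 cm.

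Do not make an interval consistent with DUH a success rule. Such a rule has no margin, ignores the sampling error in DUH's 104 bleeds, and is easier to meet the less precise the study is.

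The change takes a few sentences and needs no new patients, data or analyses. Its only cost is a less favourable claim.

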A prospective cohort study to be conducted at MRRH Division of Neurosurgery. Has emergency ward, the neurosurgery team is led by a Neurosurgeon, Emergency Medicine program with consultants, radiology department. When applicable (conscious patient and/or family or patient surrogate/attendant is present) the study will be introduced to the patient and relevant parties prior to the research team approaching the patient. While head trauma frequently results in impaired cognition and/or consciousness, and due to the urgency of these circumstances patients are often not accompanied by kin, whenever appropriate, the purpose of the research and the procedure will be explained in detail, using an IRB-approved verbal consent "script", with all questions answered to the patient's and/or representative's satisfaction. Because patients who sustain head trauma injuries typically remain within the hospital for multiple days for monitoring and care, each participant may undergo multiple CT scans over the course of his or her hospitalization, affording the opportunity to obtain one to numerous measurements from each patient during his or her hospital stay. When subjects are approached for subsequent study measurements, if the participant has regained the capacity to consent or has a patient surrogate/attendant present, the verbal script will be used to obtain consent. Participants will be asked at that time if prior measurements obtained may be used in the research

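### Scan-level rates have no interval that allows for repeat scans in one patient, and the visible text does not say which InfraScanner reading is compared with each CT

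*Combined protocol and SAP*

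**What the plan says.** Section 14 (Objectives) makes both levels of analysis part of the primary objective: "The sensitivity, specificity, and the false positive and false negative rates will be estimated at the patient level and at the scan level". It adds: "Approximately 10% of patients are anticipated to have more than one CT scan". Section 5 expects the hospital stay to yield repeated data, "affording the opportunity to obtain one to numerous measurements from each patient". The exploratory ROC curves are also planned "with patient and scan as the units of analysis". Section 14b gives sensitivity a double unit: it "will be defined for each patient (scan) as the probability" of detecting a CT-confirmed hematoma.

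One interval formula appears, under Sample Size (14c): "The 90% confidence interval for the sensitivity is given by" the estimate plus or minus 1.645 standard errors, with N the number of true positives. No clustered variance, GEE, mixed model or patient-level bootstrap is named. The interim interval in 14d is called adjusted, without saying for what.

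On the readings themselves:

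- Section 5: one reading before the CT and another after it with a second InfraScanner. The patient is scanned twice, in under 15 minutes including the greeting.
- Section 10: one scan tied to each CT, taking under 10 minutes. Section 15 also gives about 10 minutes.
- Section 14b: patients are scanned "within 30 minutes of each subsequent CT", with no number of readings and no second device. Specificity is tied to the "scan within 30 minutes of CT given the patient has no hematoma present"; sensitivity has no time window.
- Sections 5, 10 and 14b each also provide for a reading on arrival.

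**The concern.** Two gaps meet here. First, several scans from one patient are not independent, and the plan offers no interval that recognises this. The study exists to estimate test characteristics, so the interval is part of the result.

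Second, the CT is the natural scan-level unit, but the text leaves two or three candidate readings for one CT (arrival, before, after) and does not say which is compared with it. Nor does it say which CT stands for the patient when there are several. Either choice could be made after the results are known and would move the estimates themselves, not only their intervals. This second gap needs no assumption about correlation.

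**Working it through.** **The plan's own figures.** The formula reproduces them at the worst case p = 0.5, with a square root over the variance (the printed expression lacks one, perhaps lost in text extraction):

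- Sensitivity, 68 positive patients: 1.645 × √(0.25/68) = 0.0997 (stated 0.099).
- Specificity, 272 negative patients: 1.645 × √(0.25/272) = 0.0499 (stated 0.05).
- 68/0.20 = 340 patients with CT; 340/0.50 = 680; 680/0.95 = 716, close to the stated 720.

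These count patients, one result each, so clustering does not touch them.

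**Inputs for the scan level.** From section 14: 68 CT-positive and 272 CT-negative patients, about 10% with repeat CTs. From section 3: sensitivity 0.86 for bleeds of any size in the earlier single-hospital series. Assumed, because the documents are silent: two CTs per repeat patient, the 10% applying equally to positives and negatives, and a within-patient correlation ρ of 0.3 to 0.8, the same between CTs and between readings of one CT.

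**Formulas.** With m readings per patient, the design effect is D = 1 + (Σm²/Σm − 1)ρ. The true coverage of an unclustered 90% interval is approximately 2Φ(1.645/√D) − 1.

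**One reading per CT, positives.** 61 patients × 1 + 7 × 2 = 75 scans. Σm² = 61 + 28 = 89, and 89/75 = 1.187. The unadjusted half-width at 0.86 is 1.645 × √(0.86 × 0.14/75) = 0.066.

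| ρ | D | Coverage | Half-width at 0.86 |
|---|---|---|---|
| 0.3 | 1.056 | 89.1% | 0.068 |
| 0.5 | 1.093 | 88.4% | 0.069 |
| 0.8 | 1.149 | 87.5% | 0.071 |

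Specificity behaves the same way: 245 × 1 + 27 × 2 = 299 scans give 87.6% to 89.1%. With five CTs per repeat patient, sensitivity coverage would be about 74% to 83%.

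**Both section 5 readings pooled, positives.** 61 × 2 + 7 × 4 = 150 readings. Σm² = 244 + 112 = 356, and 356/150 = 2.373. The unadjusted half-width is 0.047.

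| ρ | D | Coverage | Half-width at 0.86 |
|---|---|---|---|
| 0.3 | 1.412 | 83.4% | 0.055 |
| 0.5 | 1.687 | 79.5% | 0.061 |
| 0.8 | 2.099 | 74.4% | 0.068 |

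**Form of the patient-level interval.** By exact binomial enumeration, averaged over sensitivities 0.86 to 0.94, the 14c (Wald) form covers 87.1% at n = 68 and 85.3% at n = 30, against 90.3% and 91.3% for Wilson. The 30 is the number of positives expected at the interim, 150 × 0.20. Coverage is saw-toothed: at exactly 0.86, Wald covers 90.4% and 91.8%.

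**The case against.** The case against a serious reading is good in several respects.

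- *The clustering effect is small.* With one reading per CT it costs about 1 to 2.5 points of coverage, under an assumed correlation. This stands, although more CTs per repeat patient would enlarge it.
- *A reader might infer that the reported intervals will cover only 74% to 83%.* With two CTs per repeat patient, that needs both readings pooled as separate observations, and no section plans this. Sections 5 and 10 tie the number of data collections to the number of CTs, and 14b speaks of a single scan. The figure shows what an index rule prevents; it is not a forecast.
- *A reader might infer that 14c prescribes its formula for scans.* It sits under Sample Size and is applied there to patients. The fair statement is that scan-level intervals have no stated method.
- *A reader might infer that 14b flatly contradicts section 5.* It conflicts only by implication, since it gives no count. The direct conflict is between sections 5 and 10. The different durations are what one would expect of two scans against one, so they add little.
- *The reading sequence may be set out elsewhere.* Section 8 refers to a data-collection chart that is not shown. If it names the reading compared with the CT, that part of the point is answered, though sections 5 and 10 would still need to agree.
- *The preference for Wilson is generic.* At 0.86, the closest analogue to the primary objective, the Wald form is adequate. The 0.94 end of the range comes from bleeds above 3.5 mL, where there would be fewer positives than 68 or 30.

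What remains is the absence of any clustered interval, the conflict between sections 5 and 10, and no visible rule for the index reading or the patient-level CT.

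**Conclusion.** The point holds, at moderate weight. If the 14c interval is carried over to scans, it is somewhat too narrow: 87.5% to 89.1% coverage for a nominal 90%, given one reading per CT, two CTs per repeat patient and ρ of 0.3 to 0.8. The more important part is that sections 5 and 10 disagree and the visible text names no index reading, so the primary estimates can depend on a later choice.

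It should not be read as an error in the sample size: 68, 272 and 720 stand. Nor would a formal conclusion be reversed, since no success threshold is planned. The interim results may change enrolment, however, so the undefined adjustment in 14d should be settled too.

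**What to change.** 1. Reconcile section 5 with sections 10 and 14b. Name in advance one index reading per CT, used for both sensitivity and specificity. The rule must also cover patients who arrive with a CT already taken, whom 14a admits. Report the other device's readings separately and never pool them as independent.
2. For scan-level rates, use patient-clustered intervals, for example GEE with a logit link and robust standard errors, or Wilson with the effective sample size. If no hematoma is missed, give the patient-level Wilson interval. For the scan-level AUC, use a bootstrap that resamples patients. A robust standard error in a symmetric ±1.645 form is not enough. In simulation (one reading per CT, ρ 0.5 and 0.8, sensitivities 0.85 to 0.97, an assumed range) it covered 85.4% to 86.0%, against 90.8% to 90.9% on the logit scale and 89.7% for Wilson with effective n.
3. State in advance which CT gives the patient-level result. This is a choice of estimand and belongs to the sponsor.
4. As a minor improvement, use Wilson for patient-level intervals, including at the interim, and define the adjustment in 14d.

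**Cost.** Analysis wording, recorded times for each reading and CT, and possibly a change to the collection form; no new patients or CTs. With one reading per CT, scan-level half-widths at 0.86 grow by about 0.002 to 0.005. CTs without an index reading must be counted and reported, which may leave fewer usable positives than the 68 planned; the documents do not allow that number to be estimated.
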